4.4. Discontinuations

4.4.1. Discontinuation of Study Drugs/Medications

The criteria for enrolment must be followed explicitly. If a patient who does not meet enrolment criteria is inadvertently enrolled, that patient should be discontinued from the study drugs/medications, but can be allowed to continue in the study in order to provide the follow-up data needed for the analysis of the entire population. An exception may be granted if the patient, in the opinion of the Investigator, is having benefit from the study drugs/medications. In these rare cases, the investigator must obtain documented approval from GEICAM to allow the patient to continue to receive the study drugs/medications.

Patients can be discontinued from the study therapy in the following circumstances:

- Patient's own request. The patient is at any time free to discontinue treatment, without prejudice to further treatment.
- Unacceptable toxicity as defined in the protocol.
- Any clinical adverse event (AE), laboratory abnormality or inter-current illness which, in the opinion of the investigator, indicates that continued participation in the study is not in the best interest of the patient.
- Bone marrow findings consistent with myelodysplastic syndrome (MDS)/acute myeloid leukaemia (AML)
- Pregnancy:
 - ✓ Instruct to contact the investigator or study staff immediately if they suspect they might be pregnant.
 - ✓ The investigator must immediately notify GEICAM if a study patient becomes pregnant.
- Tumour progression as defined in the protocol.
- Severe non-compliance with the study protocol by the patient
- Loss of ability to freely provide consent through imprisonment or involuntarily incarceration for treatment of either a psychiatric or physical (e.g. infectious disease) illness.
- Physician's decision, including need of other anti-cancer therapy, not specified in the protocol.
- Termination of the study by GEICAM.

All permanent treatment discontinuation should be recorded by the Investigator in the eCRF when considered as confirmed.

It is important to discriminate between discontinuation of study treatment only and withdrawal from study (study treatment and follow up).

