8.1. Determination of Sample Size

8.1.1. Sample Size Determination

We have set the null hypothesis (H0) that ORR will be 30% (ORR achieved by TN patients treated with gemcitabine plus carboplatin¹) versus the alternative hypothesis (H1) that ORR will be 54% (ORR showed by TN *BRCA* mutated patients treated with olaparib²). Using an optimal two-stage Simon model and considering an alpha error of 0.05 and a statistical power of 80%, it will be required to include 31 evaluable patients. Twelve evaluable patients will be enrolled in the first stage, and if at least 4 patients of them have response, additional patients will be recruited to get a total of 31 evaluable patients. Assuming a 10% dropout rate, the total number of patients to be enrolled is 34. Considering, these data the number of responders needed at the end of stage 2 to reject the null hypothesis is at least 14 responders.

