8.2.1. Patient Populations

Intent to treat population (ITT): The ITT population will include all patients who are enrolled in the study.

Efficacy population: a subset of the ITT population that have received at least one dose of study medication and has performed at least one tumour response assessment according to RECIST v.1.1 (unless a progression, death or unacceptable toxicity is seen before the first tumour response assessment) and without major protocol deviations according to the protocol deviation manual.

The **efficacy** population will be the primary population for the efficacy analysis.

It will be performed a sensitivity analysis using the ITT population.

Safety population: will include all patients enrolled in the study who received at least one dose of treatment. This population is for the safety analysis.

Population for Biomarker Analysis: a subset of enrolled patients with evaluable blood and/or tumour samples required for achievement of the secondary and exploratory objectives of the study.

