8.2.5. Treatment Compliance

Treatment information will be collected at each dose administration. The estimate of percent compliance will be given by:

$$\text{Percent Compliance} = \frac{\text{Actual dose administered per week}}{\text{Dose expected to be administered per week}} \times 100$$

No minimal level of compliance will be defined for patient inclusion in final efficacy analysis. In the step 1 analysis it will be necessary that the twelve included patients have received at least 80% of the planned dose. Exploratory analysis of the impact of compliance on selected efficacy endpoints may be performed if deemed necessary.

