### **4.2 Efficacy population**

A subset of the ITT population that have received at least one dose of study medication and has performed at least one tumour response assessment according to RECIST version 1.1 (unless PD, death or unacceptable toxicity is observed before the first tumour response assessment) and without major protocol deviations according to the protocol deviation manual.

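### The primary efficacy set may drop treated patients for major deviations of any timing, with response known, and if they are replaced this could inflate the type I error

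*Protocol*

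**What the plan says.** - **Primary set.** Protocol 8.2.1 (Patient Populations) asks for at least one dose and at least one RECIST assessment. The assessment is waived after early progression, death or unacceptable toxicity. Patients must also be "without major protocol deviations according to the protocol deviation manual". SAP 4.2 ends with the same condition: "and without major protocol deviations according to the protocol deviation manual". The protocol adds that this "population will be the primary population for the efficacy analysis", with ITT as a sensitivity analysis. The Efficacy population is the ORR denominator in Protocol 8.2.6.1 and SAP 9.2.1.1.
- **What is not said.** Neither document lists the major deviations, restricts them to the period before dosing, or says who classifies them, when, or with what knowledge of response.
- **Design.** Protocol 8.1.1 sets the "null hypothesis (H0) that ORR will be 30" per cent against the "alternative hypothesis (H1) that ORR will be 54" per cent, "considering an alpha error of 0.05 and a statistical power of 80" per cent. Twelve evaluable patients enter stage 1, and at least 4 responders are needed to continue to 31 evaluable patients. At least 14 responders reject the null. Enrolment is 34, to allow for 10% dropout.
- **Compliance.** Protocol 8.2.5 says "No minimal level of compliance will be defined for patient inclusion in final efficacy analysis", but requires the twelve step 1 patients to have received at least 80% of the planned dose.
- **Assessment.** Response is derived from the local reading (Protocol 8.2.6), and SAP 8.2 marks a data monitoring committee as not applicable.

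**The concern.** An exclusion with no time limit can act on events after the first dose, such as missed scans or poor adherence. These are examples, since the manual's contents are not given. It is plausible that such events are commoner in patients who are doing badly. In a single-arm trial read at the sites, nothing in the two documents prevents the classification from being made once response is known.

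The recruitment targets count evaluable patients and the success rule is a fixed number of responders. If a non-responder is ruled out and another patient takes the place, the trial has an extra chance of reaching 14. At stake are the type I error of the primary test and the size of the reported ORR.

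**Working it through.** **Inputs** (Protocol 8.1.1): null ORR 0.30, alternative 0.54, go at 4 or more of 12, success at 14 or more of 31, 34 enrolled. Room for replacement is 34 − 31 = 3 patients; 34 × 0.90 = 30.6, about 31.

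**1. The plan's own design.** The chance of success at true ORR p is

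Σ (x = 4 to 12) P[Bin(12, p) = x] × P[Bin(19, p) ≥ 14 − x].

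At p = 0.30 this is 0.0503, and at p = 0.54 it is 0.861. The chance of stopping at stage 1 under the null is P[Bin(12, 0.30) ≤ 3] = 0.493. A search for the optimal Simon design with these inputs returns 12, 31 and 14, as stated. Its stage 1 boundary is 5 rather than 4 (type I error 0.043, power 0.807), which is a separate matter. The stated rule is used below.

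**2. A fixed number of non-responders removed and replaced.** Removing k non-responders after stage 1 and replacing them leaves the responder count intact, so success means at least 14 responders among 31 + k patients. In the formula, Bin(19, p) becomes Bin(19 + k, p). At p = 0.30:

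| Non-responders replaced | Type I error |
|---|---|
| none | 0.050 |
| 1, after stage 1 | 0.064 |
| 2, after stage 1 | 0.080 |
| 3, after stage 1 | 0.098 |
| 3, all in stage 1 | 0.108 |

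In the last row the first stage becomes Bin(15, p), still with go at 4, and the chance of stopping under the null falls from 0.493 to P[Bin(15, 0.30) ≤ 3] = 0.297.

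**3. Exclusion as a rate.** The documents give no rate, so 5%, 10% and 15% are assumptions. The calculation is exact: up to 34 patients are enrolled in sequence, each may be excluded, and the first 31 retained are tested.

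| Assumed exclusion | 5% | 10% | 15% |
|---|---|---|---|
| Non-responders only | 0.066 | 0.081 | 0.092 |
| Responders and non-responders equally | 0.049 | 0.041 | 0.030 |

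With 10% of non-responders and 5% of responders excluded, the figure is 0.059. The equal-exclusion row falls below 0.050 because fewer than 31 patients may remain.

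**4. No replacement.** Suppose instead that all 34 are enrolled and every retained patient is counted against 14. Type I error is then 0.098 with no exclusion at all, and 0.100, 0.102 or 0.104 with 5%, 10% or 15% of non-responders excluded. Removing a non-responder cannot alter the final responder count, so the small increase comes only through the stage 1 look. The excess over 0.050 comes from applying a cut-off set for 31 patients to 34.

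**5. Estimate.** With 14 responders, dropping three non-responders moves the ORR from 14/34 = 41.2% to 14/31 = 45.2%.

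**6. Cut-offs for all 34 treated** (go at 4 of 12; type I error, then power): at least 14 gives 0.098, 0.924; at least 15 gives 0.053, 0.886; at least 16 gives 0.026, 0.823. Sixteen is the first cut-off at or below 0.05.

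**The case against.** - **The deviation manual is not among the documents.** It may restrict timing and set out how deviations are judged. A reader might infer that post-dosing deviations will be excluded, or that those who classify them will know the response. The documents establish neither; they only fail to rule them out. The 80% dose condition at step 1 shows that conduct after dosing can already decide who counts there, which makes the open reading reasonable but does not prove it.
- **No replacement rule is written.** Protocol 3.1.1 and 8.2.10 and SAP 8 speak of a total of 34 patients. Replacement is inferred from the targets of 12 and 31 evaluable patients. Without it, step 4 shows that exclusion adds under 0.01. This stands, and the size of the problem is conditional on it.
- **The inflation is one-directional by assumption.** Equal exclusion of responders removes it. This also stands.
- **Safeguards exist.** Progression, death or unacceptable toxicity before the first scan does not remove a patient for lack of an assessment, although the deviation condition still applies as worded. The ITT analysis counts inadequate tumour data as non-response, and major violations are summarised (Protocol 8.2.2, SAP 5.1). Selective exclusion would probably be visible, but none of these decides the trial.
- **A contradiction with Protocol 4.4.1 is tempting but weak.** That section keeps ineligible patients in follow-up "in order to provide the follow-up data needed for the analysis of the entire population", a purpose the ITT analysis serves. Nor does 8.2.5 contradict 8.2.1: having no compliance minimum in the final analysis argues against dosing shortfalls as a ground for exclusion there.

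**Conclusion.** The point holds as a statement of what the plan permits, not of what will happen. The primary set allows exclusion after dosing, with response known, on criteria found in neither document. If up to three non-responders are replaced within the 34 enrolled, type I error rises from 0.050 to between 0.064 and 0.108, at worst roughly double the stated 0.05. This rests on two assumptions: that exclusion falls mainly on non-responders, and that those excluded are replaced. Exclusion unrelated to response does not inflate the error. Selective exclusion without replacement raises the ORR estimate but not the chance of reaching 14 at the final count.

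A reader might conclude that the test is already inflated or that enlarging the primary set is enough. The first is not supported. The second is wrong, because 14 of 34 has type I error 0.098 by itself.

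**What to change.** In Protocol 8.2.1 (Patient Populations) and SAP 4.2, make the primary efficacy set all patients who received at least one dose, count those without an adequate assessment as non-responders, and keep the present Efficacy population as a sensitivity analysis. State the cut-off for the number tested:

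- test the first 12 and first 31 treated patients at 4 and 14 or more (type I error 0.050, power 0.861); or
- if all 34 treated patients are tested, require 16 or more (type I error 0.026, power 0.823).

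At minimum, limit exclusions to eligibility failures established from pre-dose data and decided without knowledge of response, and define evaluable to match at both stages.

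No new data are needed. The headline ORR may be slightly lower. The quoted power assumes an ORR of 54% among all treated patients, so it falls if some of them cannot be assessed. Because the primary analysis changes, Protocol 8.2.1 (General Considerations) calls for a protocol amendment.

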8.2.2. Patient Disposition

A detailed description of patient disposition will be provided. It will include:

- Summary of patients entered and by site.
- Total number of patients entered.
- Total number of patients enrolled.
- Summary of reasons for patients entered, but not enrolled.
- Total number of patients treated.
- Summary of reasons for patients enrolled, but not treated.

A detailed summary of reasons for patient discontinuation from study treatment will be provided.

A summary of all identified important protocol violations will be provided.

8.2.3. Patient Characteristics

Patient characteristics will include a summary of the following:

- Patient demographics.
- Baseline disease characteristics.
- Pre-existing conditions/secondary conditions.
- Prior therapy.

Other patient characteristics will be summarized as deemed appropriate.

Standard descriptive statistics, such as the mean, median, range and proportion, will be used to summarize the patient sample and to estimate parameters of interest. Ninety-five percent confidence intervals will be provided for estimates of interest where possible.

8.2.4. Concomitant Therapy

A summary of concomitant therapies will be generated in the safety population.

8.2.5. Treatment Compliance

Treatment information will be collected at each dose administration. The estimate of percent compliance will be given by:

$$\text{Percent Compliance} = \frac{\text{Actual dose administered per week}}{\text{Dose expected to be administered per week}} \times 100$$

No minimal level of compliance will be defined for patient inclusion in final efficacy analysis. In the step 1 analysis it will be necessary that the twelve included patients have received at least 80% of the planned dose. Exploratory analysis of the impact of compliance on selected efficacy endpoints may be performed if deemed necessary.

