5.4. Special Treatment Considerations. Dose Adjustments of Olaparib

All dose modifications should be based on the worst preceding toxicity.

Every effort should be made to administer study treatment at the planned dose and schedule. However, in the event of significant treatment-related toxicity, administration of olaparib may need to be adjusted as described in the following sections. Depending on the nature of the toxicity observed, dose adjustments may be required for olaparib.

In the event of significant treatment-related toxicity, olaparib dosing may be interrupted and/or reduced. Patients are to be instructed to notify Investigators at the first occurrence of any adverse sign or symptom.

All dose modifications/adjustments must be clearly documented in the patient's source notes and the appropriate section of the eCRF.

Any toxicity observed during the course of the study could be managed by interruption of the dose of study treatment or dose reductions. Repeat dose interruptions are allowed as required, for a maximum of 4 weeks on each occasion. If the interruption is any longer, the GEICAM study team must be informed. Olaparib can be dose reduced to 250 mg twice daily as a first step and to 200 mg twice daily as a second step. If the reduced dose of 200 mg twice daily is not tolerable, no further dose reduction is allowed and study treatment should be discontinued.

Once dose is reduced, escalation is not permitted.

Olaparib recommended dose modifications for treatment related toxicities requiring treatment interruption/reduction or persisting despite optimal medical treatment are described in the following sections.

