## 1. INTRODUCTION

The purpose of this Statistical Analysis Plan (SAP) is to give a detailed description of the statistical analyses to be performed to generate the final report for GEICAM/2015-06 study (COMETA-Breast).

Based on published data included in the protocol and data from the full clinical program to date, it is anticipated that olaparib, an orally active inhibitor of the enzyme poly ADP ribose polymerase (PARPi), will have a positive benefit risk profile for the treatment of the minority well-defined population of advanced triple-negative breast cancer (TNBC) patients with the promoter methylation of *BRCA* genes.

The statistical analyses of this study will be the responsibility of GEICAM. The interpretation of these results will be the responsibility of the Chief Investigator of the study.

This document may modify the plans outlined in the protocol; however, any major modifications of the primary endpoint definition and/or its analysis will also be reflected in a protocol amendment.

All analyses will be performed using the SAS Enterprise Guide 5.1 version.

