### **5.4 Treatment Compliance**

Treatment information will be collected at each dose administration. The estimate of percent compliance will be given by:

$$\text{Percent Compliance} = \frac{\text{Actual dose administered per week}}{\text{Dose expected to be administered per week}} \times 100$$

No minimal level of compliance will be defined for patient inclusion in efficacy analyses. To be considered compliant patients should have received at least 80% of the planned number of doses. Exploratory analysis of the impact of compliance on selected efficacy endpoints may be performed if deemed necessary.

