## 8. INTERIM ANALYSIS

There is no planned any interim analysis.

The optimal two stage Simon Model is carried out in two steps. The purposes of the step 1 analysis are to allow early stopping of the study for futility.

Following the two-stage Simon design, it will be reviewed whether if at least 4 of the first 12 evaluable patients show tumour response according to RECIST version 1.1, and if this occurs,

additional patients will be included to get a total of 34 patients. If 3 or less patients of the first 12 evaluable patients show an OR, recruitment will be stopped.

In case of recruitment is stopped after the step 1, it will be reviewed the feasibility and interest of performing some of the described secondary and exploratory analysis based on the available number of patients and samples.

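### The Protocol requires at least 80% of the planned dose for the twelve step 1 patients, the SAP's stopping rule has no dose condition, and the plan does not settle which applies

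*Protocol*

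**What the plan says.** Protocol 8.2.5 treats the two analyses differently. For the last one, "No minimal level of compliance will be defined for patient inclusion in final efficacy analysis". For the first, "In the step 1 analysis it will be necessary that the twelve included patients have received at least 80% of the planned dose". This is the only place where the Protocol states the dose condition; 3.1.1, 8.1.1 and 8.2.10 refer only to twelve evaluable patients.

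SAP 5.4 carries the same paragraph without the word for final and without the step 1 sentence: "No minimal level of compliance will be defined for patient inclusion in efficacy analyses". The 80% figure survives only as a label, and it is counted in doses rather than dose: "To be considered compliant patients should have received at least 80% of the planned number of doses". SAP 8 then gives the operative rule: "If 3 or less patients of the first 12 evaluable patients show an OR, recruitment will be stopped".

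Neither document defines the evaluable set for step 1. The nearest definition is the Efficacy population (Protocol 8.2.1, SAP 4.2). It needs one dose and one tumour assessment, sets no dose minimum, and waives the assessment by its clause "unless PD, death or unacceptable toxicity is observed before the first tumour response assessment".

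On precedence, SAP 1 allows the SAP to modify the Protocol's plans but adds that "any major modifications of the primary endpoint definition and/or its analysis will also be reflected in a protocol amendment". SAP 7.3 names a first database lock for step 1 and, separately, a lock for the efficacy analysis.

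**The concern.** Step 1 is the trial's only planned decision to stop. A patient below 80% is outside the twelve if Protocol 8.2.5 governs and inside if SAP 8 is read as it stands, so the count compared with the cut-off of 4 responders can differ.

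Two features raise the stakes. First, patients who stop early for toxicity or death tend both to have taken little drug and not to have responded. Removing them from the twelve tilts step 1 towards continuing, which matters most if the drug is inactive. Second, the trial is single-arm, response is read locally (Protocol 8.2.6, SAP 9.2) and SAP 8.2 provides no monitoring committee. Whoever resolves the ambiguity at step 1 may already know the responses.

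**Working it through.** **Design as written.** Inputs from Protocol 8.1.1 and SAP 3.1: null ORR 30%, alternative 54%, continue with at least 4 of 12, reject with at least 14 of 31. Exact binomial results:
- P(stop at step 1) = P(Bin(12, p) ≤ 3) = 0.4925 at 30% and 0.0415 at 54%. P(continue) is therefore 0.5075 and 0.9585.
- P(reject) = Σ over x from 4 to 12 of P(Bin(12, p) = x) × P(Bin(19, p) ≥ 14 − x) = 0.0503 at 30% and 0.861 at 54%.

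**One low-dose patient among the first twelve, replaced by the thirteenth.** The decision flips only if the other eleven contain exactly 3 responders: P(Bin(11, p) = 3) = 0.257 at 30% and 0.052 at 54%.
- She did not respond and her replacement does (SAP 3/12, stop; Protocol 4/12, continue): 0.257 × 0.30 = 0.077 at 30%; 0.052 × 0.54 = 0.028 at 54%.
- She responded and her replacement does not (SAP 4/12, continue; Protocol 3/12, stop): 0.257 × 0.70 = 0.180 at 30%; 0.052 × 0.46 = 0.024 at 54%.

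**Random number of low-dose patients.** Let q be the share below 80% (assumed, not in the documents), px their response rate, and pk = (p − q·px)/(1 − q) the rate in the rest, so that the overall ORR stays at p. Let K ~ Bin(12, q) be the low-dose patients among the first twelve, A ~ Bin(12 − K, pk) responders common to both sets, B ~ Bin(K, px) those counted only under the SAP, and C ~ Bin(K, pk) those among the replacements under the Protocol. The decisions differ when exactly one of A + B and A + C reaches 4. P(continue) under the Protocol is P(Bin(12, pk) ≥ 4).

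| q | Differ, ORR 30%, px = p | Differ, ORR 30%, px = 0 | Protocol P(continue), ORR 30%, px = 0 | Differ, ORR 54%, px = p | Differ, ORR 54%, px = 0 |
|---|---|---|---|---|---|
| 2% | 0.025 | 0.019 | 0.526 | 0.006 | 0.006 |
| 5% | 0.058 | 0.048 | 0.555 | 0.014 | 0.015 |
| 10% | 0.106 | 0.099 | 0.607 | 0.024 | 0.026 |
| 15% | 0.145 | 0.154 | 0.661 | 0.032 | 0.034 |

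With px = p, P(continue) is the same under both rules and the disagreements split equally in the two directions. With px = 0, every disagreement is SAP stop, Protocol continue. At half the overall response rate (px = 0.15, ORR 30%), Protocol P(continue) is 0.532, 0.558 and 0.587 for q = 5%, 10% and 15%.

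**Overall type I error.** With the Protocol's step 1 set and px = 0, simulation gives 0.051 to 0.052 for q = 5% to 15%, against 0.0503 exactly with the SAP set.

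**Who falls below 80% depends on undefined terms.** Tumour assessments come every 8 weeks (56 days), and confirmation at least 28 days later (day 84). Neither is named as the window for the 80%. Protocol 5.4 says "Repeat dose interruptions are allowed as required, for a maximum of 4 weeks on each occasion", and it allows reduction to 200 mg b.i.d.
- Denominator = full schedule, 56 days: 12 days off gives 44/56 = 78.6%, a failure; 11 days off gives 45/56 = 80.4%.
- Denominator = full schedule, 84 days: 17 days off gives 67/84 = 79.8%, a failure.
- Denominator = 600 mg/day, 56 days: 200 mg b.i.d. after day 22 gives (22 × 600 + 34 × 400)/(56 × 600) = 79.8%, a failure. Counted in number of doses, as in SAP 5.4, the same patient has 100%.
- Denominator = dose expected after permitted changes: none of these patients fails.

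**The case against.** The strongest reply is that the SAP omits the rule rather than withdrawing it. SAP 7.3 separates the step 1 lock from the lock for efficacy analysis, so the waiver in SAP 5.4 can be read as covering only the latter, the same scope as the Protocol's waiver. Since major changes to the primary analysis need an amendment, the Protocol rule would then stand and the SAP would lack one sentence. This reading is possible, so a reader should not infer that the SAP has overridden the Protocol. It does not remove the problem: SAP 8 would still omit a condition needed to apply its own rule.

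Second, a reader might infer that the same twelve patients can give both answers. They cannot. With one of twelve below 80%, the Protocol rule leaves eleven and no decision until another patient is added. The conflict concerns one enrolled cohort, and taking the next patient in order is an assumption.

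Third, the compliance formula in Protocol 8.2.5 divides by the dose expected. If that follows permitted changes, managed interruptions and reductions pass, and perhaps early stoppers too. The point has force, but the step 1 sentence refers to the planned dose, so the denominator remains open.

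Fourth, the shares may be small. The Protocol's reference points (6.6% discontinuing for adverse events in the tablet pool, 8.3% interrupting for anaemia) cover whole treatment periods, and the 8.3% is not limited by length of interruption. That is why the range starts at 2%.

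Finally, requiring adequate exposure at a futility look is defensible: it guards against stopping a drug that patients did not take. This stands, and the 80% rule need not be deleted.

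**Conclusion.** The concern holds as a gap between the two documents on the trial's only stopping decision. For assumed low-dose shares of 2% to 15%, the two readings disagree in about 2% to 15% of trials at ORR 30% and about 0.6% to 3.4% at 54%. If low-dose patients never respond, early stopping of an inactive drug falls from 49.3% to between 47.4% (q = 2%) and 33.9% (q = 15%). That is an upper bound; if dose is unrelated to response, the chance of continuing does not change. These figures rest on the assumed shares and on replacement in order of enrolment.

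A reader might infer that the final efficacy claim is compromised. It is not: type I error stays at about 5%, and neither document sets a dose minimum for the final ORR analysis. Nor do the documents show that anyone intends to choose the rule after seeing responses; they only leave that possible. This should be fixed before the step 1 lock, but it does not undermine the design.

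**What to change.** State one rule in both Protocol 8.2.5 and SAP 8 before the step 1 database lock.

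If the 80% condition is kept:
- add it to SAP 8;
- define the denominator as the dose prescribed after changes under Protocol 5.4 or 5.5.2;
- state the time window over which it is measured;
- replace an excluded patient with the next in order of enrolment;
- count patients who stop for progression, death or toxicity among the twelve, as non-responders unless they had already responded.

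The last item removes the selection that favours continuing an inactive drug.

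Dropping the condition and using the first twelve of the Efficacy population, in order of enrolment, is an acceptable alternative and would match the population for the final 14-of-31 rule. It is the sponsor's choice. At ORR 54%, P(continue) would be 95.9%, against 97.3% to 99.2% with the 80% rule if 5% to 15% are low-dose and none respond.

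The cost is a few sentences in each document. Keeping the rule needs a SAP revision and a short Protocol clarification; dropping it needs a Protocol amendment. No new data are required, because reductions, interruptions, missed doses and their reasons already go into the eCRF (Protocol 5.4.3).
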